8.3.4 TIME PERIOD AND FREQUENCY FOR EVENT ASSESSMENT AND FOLLOW-UP

The occurrence of an adverse event (AE) or serious adverse event (SAE) may come to the attention of study personnel during study visits and interviews of a study participant presenting for medical care, or upon review by a study monitor.

All AEs including local and systemic reactions not meeting the criteria for SAEs will be captured on the appropriate case report form (CRF). Information to be collected includes event description, time of onset, clinician's assessment of severity, relationship to study product (assessed only by those with the

training and authority to make a diagnosis), and time of resolution/stabilization of the event. All AEs occurring while on study must be documented appropriately regardless of relationship. All AEs will be followed to adequate resolution.

Any medical condition that is present at the time that the participant is screened will be considered as baseline and not reported as an AE. However, if the study participant's condition deteriorates at any time during the study, it will be recorded as an AE.

Changes in the severity of an AE will be documented to allow an assessment of the duration of the event at each level of severity to be performed. AEs characterized as intermittent require documentation of onset and duration of each episode.

Study research coordinators will record all reportable events with start dates occurring any time after informed consent is obtained until 7 (for non-serious AEs) or 30 days (for SAEs) after the last day of study participation. At each study visit, the investigator will inquire about the occurrence of AE/SAEs since the last visit. Events will be followed for outcome information until resolution or stabilization.

8.3.5 SERIOUS ADVERSE EVENT REPORTING

The study clinician will immediately report to the sponsor any serious adverse event, whether or not considered study intervention related, including those listed in the protocol or investigator brochure and must include an assessment of whether there is a reasonable possibility that the study intervention caused the event. Study endpoints that are serious adverse events (e.g., all-cause mortality) must be reported in accordance with the protocol unless there is evidence suggesting a causal relationship between the study intervention and the event (e.g., death from anaphylaxis). In that case, the investigator must immediately report the event to the sponsor.

All serious adverse events (SAEs) will be followed until satisfactory resolution or until the site investigator deems the event to be chronic or the participant is stable. Other supporting documentation of the event may be requested by the Data Coordinating Center (DCC)/study sponsor and should be provided as soon as possible.

The study sponsor will be responsible for notifying the Food and Drug Administration (FDA) of any unexpected fatal or life-threatening suspected adverse reaction as soon as possible, but in no case later than 7 calendar days after the sponsor's initial receipt of the information. In addition, the sponsor must notify FDA and all participating investigators in an Investigational New Drug (IND) safety report of potential serious risks, from clinical trials or any other source, as soon as possible, but in no case later than 15 calendar days after the sponsor determines that the information qualifies for reporting.

8.4 UNANTICIPATED PROBLEMS

8.4.1 DEFINITION OF UNANTICIPATED PROBLEMS (UP)

The Office for Human Research Protections (OHRP) considers unanticipated problems involving risks to participants or others to include, in general, any incident, experience, or outcome that meets all of the following criteria:

- Unexpected in terms of nature, severity, or frequency given (a) the research procedures that are described in the protocol-related documents, such as the Institutional Review Board (IRB)-approved research protocol and informed consent document; and (b) the characteristics of the participant population being studied;
- Related or possibly related to participation in the research (“possibly related” means there is a reasonable possibility that the incident, experience, or outcome may have been caused by the procedures involved in the research); and
- Suggests that the research places participants or others at a greater risk of harm (including physical, psychological, economic, or social harm) than was previously known or recognized.

8.4.2 UNANTICIPATED PROBLEM REPORTING

The investigator will report unanticipated problems (UPs) to the reviewing Institutional Review Board (IRB). The UP report will include the following information:

- Protocol identifying information: protocol title and number, PI’s name, and the IRB project number;
- A detailed description of the event, incident, experience, or outcome;
- An explanation of the basis for determining that the event, incident, experience, or outcome represents an UP;
- A description of any changes to the protocol or other corrective actions that have been taken or are proposed in response to the UP.

To satisfy the requirement for prompt reporting, UPs will be reported using the following timeline:

- UPs that are serious adverse events (SAEs) will be reported to the IRB 24 hours of the investigator becoming aware of the event.
- Any other UP will be reported to the IRB and to the DCC/study sponsor within 7 days of the investigator becoming aware of the problem.

9 STATISTICAL CONSIDERATIONS

9.1 STATISTICAL HYPOTHESES

- Primary Efficacy Endpoint(s):

Omega-3 fatty acid supplementation results in a decrease in the area under the concentration versus time curve for neurofilament light chain, CRP, IL-6 and IL-10 during the 3 months following TBI and an increase in the area under the concentration curve for brain derived neurotrophic factor.

- Secondary Efficacy Endpoint(s):

Omega-3 fatty acid supplementation improves functional outcome, post-concussive symptoms and cognitive decline post-TBI

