1 PROTOCOL SUMMARY

1.1 SYNOPSIS

Title:	Pilot Study of Omega-3 Polyunsaturated Fatty Acid Treatment in Mild Acute TBI (OPTIMA-TBI pilot).
Study Description:	This is a double-blinded randomized control trials comparing the effect of omega-3 fatty acid versus placebo on blood biomarkers of brain injury, inflammation and neurogenesis.
Objectives:	
Primary Objective: Biomarker endpoints include: neuronal injury measured by Neurofilament light chain (NFL), Neurogranin (NRGN) and Intercellular adhesion molecule 5 [ICAM5]; inflammation measured by high sensitivity C-reactive protein (CRP), IL-6 and IL-10 and neurogenesis measured by brain derived neurotrophic factor (BDNF)
 
Secondary Objectives:
 
1. Delayed functional recovery defined as Glasgow Outcome Scale Extended (GOSE)<8 at 3 months2. Moderate/severe post-concussive symptoms at 3 months defined as having at least three symptoms in at least three following ICD-10 symptom categories obtained from the Rivermead Post-Concussion Questionnaire (RPQ): (1) headaches, dizziness, general malaise, excessive fatigue, or noise intolerance; (2) irritability, emotional lability, depression, or anxiety; (3) subjective complaints of concentration or memory difficulty; (4) insomnia; (5) reduced tolerance to alcohol; (6) preoccupation with these symptoms and fear of permanent brain damage.3. Cognitive impairment at 3 months is defined based on a battery of 13 neurocognitive tests. Subjects are deemed cognitively impaired if their scores on at least 2 neurocognitive tests are more than 2 standard deviations below their IQ T-Score ascertained by the Wechsler Test of Adult Reading (WTAR).4. Serious adverse events (SAEs): Life-threatening bleed including upper GI bleed, intracranial hemorrhage; hypotension; severe allergic reaction, blood glucose and LDL cholesterol levels
Endpoints:	
Primary Endpoint: Serum levels of neurofilament light chain, C-reactive protein, IL-6, IL-10, Brain derived neurotrophic factor over a 3-month period
 
Secondary Endpoints: Functional recovery (measured by Glasgow Coma Scale Extended), symptomatic recovery (measured by the Rivermead Post-concussive Symptoms Questionnaire) and cognitive impairment (measured by a cognitive battery) at 3 months post injury

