3 OBJECTIVES AND ENDPOINTS

OBJECTIVES	ENDPOINTS	JUSTIFICATION FOR ENDPOINTS
Primary		
To determine the effect of omega-3 polyunsaturated fatty acids (PUFA) treatment on blood biomarkers of neuronal injury and blood biomarkers of inflammation and a blood biomarker of neurogenesis	Neurofilament light chain [NFL], Neurogranin [NRGN] and Intercellular adhesion molecule 5 [ICAM5], high sensitivity C-reactive protein [CRP], IL-6, IL-10, and brain derived neurotrophic factor [BDNF]	If omega-3 fatty acid supplementation decreases the levels of biomarkers of neuronal injury and inflammation and increases the levels of biomarkers of neurogenesis, then there is a strong likelihood it will improve clinical outcome
Secondary		

 1. To demonstrate the feasibility of enrolling, treating and conducting follow-up assessments on mTBI patients presenting to the University of Michigan 2. To acquire preliminary data on the effect of omega-3 PUFA treatment on delayed functional recovery, moderate/severe post-concussive symptoms and cognitive impairment. 3. To acquire preliminary data on the types and incidence of serious adverse events (SAEs) in the Omega-3 PUFA treatment arm compared to the placebo arm 	
 1. Successful enrollment of 50 subjects within 1 year 2. Measurement of functional recovery using the Glasgow Outcome Scale Extended (GOSE), measurement of symptomatic recovery using the Rivermead Post-concussive symptoms questionnaire (RPQ) and cognitive impairment using a neurocognitive battery of tests 3. Measurement of the incidents of gastrointestinal distress and clinically significant bleeding 	These endpoints will help inform the design of a multi-center phase II trial

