4 STUDY DESIGN

4.1 OVERALL DESIGN

We hypothesize that treatment of traumatic brain injury patients with omega-3 fatty acids will result in a decrease in blood concentrations of biomarkers of neuronal injury and inflammation and an increase in the blood concentration of biomarkers of neurogenesis. This is a randomized, placebo-controlled, double-blinded pilot phase II clinical trial. Participants will be randomized either a single dose of 6g of DHA+EPA for 1 month followed by 1.2g/day of DHA+EPA for two additional months or to placebo treatment for 3 months. Blood samples will be drawn at enrollment, 2 weeks, 1 month and 3 months post-injury. Biomarkers of neuronal injury, inflammation, and neurogenesis will be measured in batches. Functional and symptomatic recovery will be assessed at 2 weeks, 1 month and 3 months. Additionally, cognitive impairment will be assessed at 3 months.

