9.3 STATISTICAL ANALYSES

9.4.1 GENERAL APPROACH

We will examine blood levels of biomarkers of omega-3 intake, axonal injury, and inflammation (red blood cell and plasma omega-3 index, NFL, ICAM5, CRP, IL-6 and IL-10) at baseline and at 3 months in both the intervention and the control groups and test the hypothesis that omega-3 PUFA treatment increases omega-3 PUFA blood levels and decreases levels of biomarkers of axonal injury and inflammation. To examine the effect of omega-3 PUFA treatment on biomarkers of neuronal injury and inflammation, we will construct multiple linear regression models with generalized estimating equations (GEE) and robust variance estimation to account for correlations within repeated measurements. This will allow us to determine whether variations in the levels of NFL, ICAM5, CRP, IL-6 and IL-10 over the 3 month study period differ among those receiving omega-3 PUFA supplementation versus those receiving placebo.

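### The primary hypothesis is a 3-month AUC that includes BDNF, but the only analysis text specifies no AUC, names no primary contrast and does not analyse BDNF

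*Combined protocol and SAP*

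**What the plan says.** Section 9.1 (Statistical Hypotheses) expects "a decrease in the area under the concentration versus time curve for neurofilament light chain, CRP, IL-6 and IL-10" during the 3 months after TBI, and "an increase in the area under the concentration curve for brain derived neurotrophic factor". Section 4.1 (Overall Design) likewise hypothesises "an increase in the blood concentration of biomarkers of neurogenesis".

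The synopsis (1.1) gives the primary endpoint as "Serum levels of neurofilament light chain, C-reactive protein, IL-6, IL-10, Brain derived neurotrophic factor over a 3-month period". That row names five markers and speaks of levels, not AUC. The synopsis objective lists seven markers, adding NRGN and ICAM5. Section 3 also lists seven: "Neurofilament light chain [NFL], Neurogranin [NRGN] and Intercellular adhesion molecule 5 [ICAM5], high sensitivity C-reactive protein [CRP], IL-6, IL-10", followed in the same cell by BDNF. Section 8.1 names an assay for all seven.

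The analysis text is one paragraph in section 9.3, under the sub-heading 9.4.1 (General Approach). It describes two analyses:
- an examination of marker levels "at baseline and at 3 months in both the intervention and the control groups";
- linear models fitted by GEE with robust variance, to "determine whether variations in the levels of NFL, ICAM5, CRP, IL-6 and IL-10 over the 3 month study period differ" between arms.

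Both of its lists name NFL, ICAM5, CRP, IL-6 and IL-10 (the first adds the omega-3 index). Neither names BDNF or NRGN.

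**The concern.** A primary hypothesis needs a stated analysis that estimates the quantity it names, for every marker it names. Here the hypothesis is about an AUC and the analysis text is not. The one marker meant to show neurogenesis is assayed but has no analysis.

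At stake are a part of the primary objective that would go untested and, for the other markers, a choice between summary measures made once the data are in hand. Those measures need not agree, so the choice can alter the size of the reported effect.

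**Working it through.** The plan gives no figure on this point to reproduce. Section 9.2 states 50 patients without alpha, power, effect size or SD. The check is a comparison of the lists, then the weights that an AUC would imply.

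**Step 1. Marker lists side by side**

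| Marker | 1.1 objective | 1.1 endpoint | 3 | 8.1 assay | 9.1 | 9.3 |
|---|---|---|---|---|---|---|
| NFL, CRP, IL-6, IL-10 | yes | yes | yes | yes | yes | yes |
| BDNF | yes | yes | yes | yes | yes | **no** |
| NRGN | yes | no | yes | yes | no | not named; marker class only |
| ICAM5 | yes | no | yes | yes | no | yes |

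Four of the seven markers appear everywhere. BDNF is missing only from the analysis. Section 9.3 refers to omega-3 intake, axonal or neuronal injury and inflammation. It never refers to neurogenesis, so no reading of it reaches BDNF.

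**Step 2. What the GEE could estimate**

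Blood is drawn at enrollment, 2 weeks, 1 month and 3 months (4.1). A GEE with categorical visit and arm-by-visit terms gives a between-arm difference at each visit, and a weighted sum of these is an AUC contrast. A linear trend by arm would give a difference in slopes instead. Section 9.3 states neither the time coding nor the contrast.

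**Step 3. Trapezoid weights**

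Assumptions: follow-up visits at days 14, 30 and 90, and the enrollment draw at day t0 between 0 and 7 (5.1 and 5.2 allow up to 7 days after injury). The weights are (14 − t0)/2, (30 − t0)/2, (90 − 14)/2 and (90 − 30)/2, divided by 90 − t0.

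- t0 = 0: (7, 15, 38, 30)/90 = 7.8%, 16.7%, 42.2%, 33.3%. The 2-week and 1-month draws together: 53/90 = 58.9%.
- t0 = 7: (3.5, 11.5, 38, 30)/83 = 4.2%, 13.9%, 45.8%, 36.1%. Together: 49.5/83 = 59.6%.

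The baseline/3-month comparison gives these two draws zero weight.

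**Step 4. Does the choice matter?**

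Assume between-arm differences of 0 at enrollment, −1 at 2 weeks and 1 month, and −f at 3 months. The time-averaged AUC difference is −(53 + 30f)/90 for t0 = 0 and −(49.5 + 30f)/83 for t0 = 7. The baseline/3-month difference is −f.

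| f | AUC, t0 = 0 | AUC, t0 = 7 | Baseline/3-month |
|---|---|---|---|
| 1 | −0.92 | −0.96 | −1.00 |
| 0.5 | −0.76 | −0.78 | −0.50 |
| 0 | −0.59 | −0.60 | 0 |

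The two measures nearly agree if the difference is constant after baseline, and diverge if it fades. The documents give no data on which pattern applies.

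**The case against.** The best defence is that this is an unpowered pilot of 50 and that the GEE suits the endpoint. It is introduced expressly to examine the treatment effect over the 3-month period, which matches the synopsis wording, and it can use every draw and yield an AUC contrast. That stands. A reader might infer that the plan discards some 60% of the information for NFL, CRP, IL-6 and IL-10. It does not: the 59-60% figure applies only if the baseline/3-month examination is taken as the answer. What remains is that no contrast is stated and neither analysis is named primary. Pilot status lowers the stakes but does not supply the missing analysis, since 9.1 states directional primary hypotheses and 9.3 promises a test.

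Three stronger readings are not supported:

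- **NRGN has no analysis at all.** The GEE sentence refers to neuronal injury markers as a class, and the synopsis puts NRGN in that class. Both explicit lists in 9.3 omit it, so its status is ambiguous rather than settled.
- **Section 9.1 is the section in error on ICAM5.** The synopsis objective, section 3 and section 9.3 include it; the synopsis endpoint row and 9.1 do not. This is a conflict, and the text does not show which list was intended.
- **Follow-up draws may be up to 14 days late, making the weights far less certain.** Section 7.3 can equally be read as a deadline for contacting the participant and rescheduling, so no range is built on it here.

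**Conclusion.** The point holds in this form. The primary hypothesis in 9.1 has no matching specified analysis, and for BDNF there is none at all. That rests on the text alone and needs no assumption. BDNF is 1 of the 5 markers in 9.1 and the whole of the neurogenesis part.

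For NFL, CRP, IL-6 and IL-10 the defect is narrower: the quantity that answers 9.1 is left open. Its possible size (59-60% of trapezoid weight unused, and the differences tabulated above) depends on the assumed visit days, on assumed effect patterns and on the baseline/3-month comparison being the one chosen.

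The marker lists conflict on NRGN and ICAM5 and must be reconciled. BDNF and the unnamed primary contrast must be fixed. Rules for visit timing are a lesser clarification.

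**What to change.** 1. Add BDNF to the GEE in section 9.3.
2. Use one primary marker list in both synopsis rows (1.1) and in sections 3, 9.1 and 9.3. The sponsor decides whether NRGN and ICAM5 are primary or secondary. Every listed marker gets an analysis.
3. Name one primary contrast, by either route:
   - (a) Keep the AUC. Fit the GEE with categorical visit and arm-by-visit terms, adjusted for the enrollment value or with enrollment means constrained equal across arms. Test the trapezoid-weighted contrast from enrollment to 3 months with a small-sample variance correction. Say in 9.1 that the AUC starts at enrollment: up to 7 of 90 days (7.8%) after injury have no sample, and carrying the enrollment value back would assume flat levels over that time.
   - (b) Reword 9.1 to the specific between-arm contrast that the GEE estimates, with its time coding.
4. Label the baseline/3-month comparison secondary.

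The variance correction in (a) has a modest but visible effect. A simulation assumed 25 per arm, complete data, exchangeable correlation of 0.3 to 0.8 and no baseline adjustment, with 20,000 runs per setting. The uncorrected robust test of the AUC contrast rejected a true null in 6.0-6.5% of runs at a nominal two-sided 5%. An n/(n − 1) correction with a t reference gave 5.0-5.3%.

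The cost is wording in four places and one contrast per marker, with no new draws or assays. If NRGN and ICAM5 both become primary, there are seven primary tests instead of five. Assuming independent 5% tests, the chance of at least one false positive rises from 1 − 0.95^5 = 23% to 1 − 0.95^7 = 30%. The plan should acknowledge this.

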9.2 SAMPLE SIZE DETERMINATION

This is a pilot study of 50 patients.

9.3 STATISTICAL ANALYSES

9.4.1 GENERAL APPROACH

We will examine blood levels of biomarkers of omega-3 intake, axonal injury, and inflammation (red blood cell and plasma omega-3 index, NFL, ICAM5, CRP, IL-6 and IL-10) at baseline and at 3 months in both the intervention and the control groups and test the hypothesis that omega-3 PUFA treatment increases omega-3 PUFA blood levels and decreases levels of biomarkers of axonal injury and inflammation. To examine the effect of omega-3 PUFA treatment on biomarkers of neuronal injury and inflammation, we will construct multiple linear regression models with generalized estimating equations (GEE) and robust variance estimation to account for correlations within repeated measurements. This will allow us to determine whether variations in the levels of NFL, ICAM5, CRP, IL-6 and IL-10 over the 3 month study period differ among those receiving omega-3 PUFA supplementation versus those receiving placebo.

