4.3 JUSTIFICATION FOR DOSE

Some animal studies have used a dose of 40mg/kg. Human studies of high dose omega-3 fatty acids for preventing cardiovascular disease have used our study dose of 4g. The maximum tolerable dose of omega-3 fatty acids is 21g/day. Case reports of severe TBI treatment with omega-3 fatty acids have reported using up to 19g/day. In our population of mild TBI patients we have selected a dose of 6g/day which is about 2 times the dose used in animal studies but significantly below the maximum tolerable dose or the dose used in other TBI studies.

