6 STUDY INTERVENTION

6.1 STUDY INTERVENTION(S) ADMINISTRATION

6.1.1 STUDY INTERVENTION DESCRIPTION

The study intervention is an omega-3 fatty acid capsules manufactured by Wiley's Finest. We will utilize a formulation that contains 500 mg of docosahexaenoic acid (DHA) and 100 mg of eicosapentaenoic acid (EPA) in one capsule

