6.1.2 DOSING AND ADMINISTRATION

Every attempt will be made to start treatment as soon as possible after enrollment. The first dose will be administered within 7 days of injury. The intervention group will receive 6g per day of DHA+EPA for 1 month followed by 1.2 g/day of EPA+DHA for two additional months. The control group will receive placebo treatment for 3 months.

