6.4 STUDY INTERVENTION COMPLIANCE

Adherence to protocol will be assessed by measuring plasma levels of EPA and DHA and red blood cell index of omega-3 fatty acids at each follow-up visit.

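### The only planned test of omega-3 exposure is at 3 months, the one visit under 1.2 g/day; the 2-week and 1-month levels already measured should be compared in the same GEE

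*Combined protocol and SAP*

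**What the plan says.** **Regimen.** Section 6.1.2 gives the active arm 6 g per day of DHA+EPA for one month, "followed by 1.2 g/day of EPA+DHA for two additional months". The first dose falls within 7 days of injury. Section 4.3 argues for the higher dose: "we have selected a dose of 6g/day which is about 2 times the dose used in animal studies".

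**Sampling.** Section 4.1: "Blood samples will be drawn at enrollment, 2 weeks, 1 month and 3 months post-injury". The schedule of activities in 1.3 agrees.

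**Exposure data.** Section 6.4 assesses adherence by "measuring plasma levels of EPA and DHA and red blood cell index of omega-3 fatty acids at each follow-up visit". It names no between-arm comparison, model or threshold for these values.

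**Exposure test.** Section 9.4.1 takes the red-cell and plasma omega-3 index together with NFL, ICAM5, CRP, IL-6 and IL-10 and tests them "at baseline and at 3 months in both the intervention and the control groups and test the hypothesis that omega-3 PUFA treatment increases" omega-3 levels and lowers the markers.

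**Longitudinal model.** The GEE in 9.4.1 asks whether "variations in the levels of NFL, ICAM5, CRP, IL-6 and IL-10 over the 3 month study period" differ between the arms. The omega-3 measures are not in that list. Section 9.1 states its primary hypothesis as a fall in the "area under the concentration versus time curve for neurofilament light chain, CRP, IL-6 and IL-10 during the 3 months following TBI" (with a rise for BDNF) and has no hypothesis on exposure.

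**The concern.** The dose changes five-fold after one month, so exposure has two phases. The GEE and the AUC hypothesis use marker values from both. The one planned exposure test uses a sample from the second phase only, well after the step-down.

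A raised omega-3 level at 3 months can arise from intake in months 2 and 3 alone, so it does not show that the 6 g/day month was taken. Conversely, a small difference at 3 months is compatible with full intake in month 1. Section 3 says that the endpoints are meant to inform a multi-center trial. If the markers show no effect, its designers will first ask whether the high-dose month produced the intended separation between the arms. The values that answer this will be in the database, but the plan compares them nowhere.

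**Working it through.** The plan's only design figure is a sample size of 50 (9.2), given without inputs. There is nothing to reproduce, and the point does not depend on it.

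**1. What is measured against what is compared**

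| Visit | Omega-3 measured | Omega-3 in a named test (9.4.1) | Markers in the GEE (9.4.1) |
|---|---|---|---|
| Enrollment | yes, implied by 9.4.1 | yes | yes |
| 2 weeks | yes (6.4) | no | yes |
| 1 month | yes (6.4) | no | yes |
| 3 months | yes (6.4) | yes | yes |

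Two of the three follow-up measurement occasions per participant enter no planned comparison.

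**2. Which dose each visit falls under**

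Inputs: first dose on day 0 to 7 (6.1.2); visits timed from injury (4.1). Months of 30 days are assumed, so the visits fall on days 14, 30 and 90.

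- End of the 6 g/day phase: 0 + 30 = day 30, to 7 + 30 = day 37.
- 2-week draw: 14 − 7 = 7, to 14 − 0 = 14 days at 6 g/day.
- 1-month draw: 30 − 7 = 23, to 30 − 0 = 30 days at 6 g/day.
- 3-month draw: 90 − 37 = 53, to 90 − 30 = 60 days at 1.2 g/day.

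**3. Size of the step-down**

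The capsule holds "500 mg of docosahexaenoic acid (DHA) and 100 mg of eicosapentaenoic acid (EPA) in one capsule", or 0.6 g. The dose goes from 6/0.6 = 10 capsules a day to 1.2/0.6 = 2. The planned intake is 6 × 30 = 180 g in month 1 and 1.2 × 60 = 72 g in months 2 and 3, so 180/252 = 71% falls in the phase that has no planned exposure comparison.

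**4. How much the 3-month level says about month 1 (illustration)**

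The documents give no half-life. Assume first-order kinetics, a start on day 0 and half-life h in days, with f(t) = 2^(−t/h), in relative units.

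- Level at 1 month: L1 = 6 × (1 − f(30)).
- Level at 3 months: L3 = L1 × f(60) + 1.2 × (1 − f(60)).
- Share of L3 that comes from month 1: L1 × f(60) / L3.

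| h (days) | L1 | L3 = month 1 part + later part | Share from month 1 |
|---|---|---|---|
| 7 | 5.69 | 0.015 + 1.197 = 1.21 | 1% |
| 14 | 4.64 | 0.238 + 1.138 = 1.38 | 17% |
| 28 | 3.14 | 0.712 + 0.928 = 1.64 | 43% |
| 56 | 1.86 | 0.886 + 0.629 = 1.51 | 58% |

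With a start on day 7 (53 days at 1.2 g/day by day 90) the shares are 2%, 23%, 49% and 63%. With a short half-life, the 3-month level hardly registers month 1. With a long one, it mixes the two phases. Over this range it never isolates the 6 g/day phase, while the 1-month sample does so directly.

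**The case against.** **Section 6.4 already covers month 1.** This is the strongest reply, and much of it stands. Adherence can be judged descriptively and per participant, and the investigators will hold the 2-week and 1-month values. A reader might infer that exposure in the high-dose month goes unchecked; 6.4 shows that this is wrong. What remains is narrower: 9.4.1 does set out an omega-3 comparison, and it confines it to baseline and 3 months.

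**The 3-month comparison is internally matched.** The same sentence of 9.4.1 compares the markers at baseline and 3 months, so exposure and response are aligned there. This stands. The mismatch concerns only the GEE and the AUC hypothesis.

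**The kinetics are inconclusive.** The half-life is assumed, and the share runs from 1% to 58%. With long half-lives the 3-month test does carry month-1 information. This also stands; the point claims only that the test does not assess that phase directly.

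**Stronger readings that the documents do not support:**
- *That the marker result leans mainly on the 6 g/day samples.* A trapezoidal AUC might suggest this, but no AUC method is stated. The day-30 sample's trapezoid weight would be (30 − 14)/2 + (90 − 30)/2 = 8 + 30 = 38 days, of which 30 come from the 1.2 g/day interval.
- *That 2 × 50 = 100 unused samples were taken under 6 g/day.* That count includes the placebo arm, and no allocation ratio is given.
- *That 1.2 g/day is too low, because no reason is given for it.* None of the doses cited in 2.2 or 4.3 is presented as a minimum effective dose. The absent reason is missing detail, not evidence against the regimen.

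**Conclusion.** The point holds as a minor gap in the analysis plan, not in data collection. The only planned test of omega-3 levels rests on the single visit under the lower dose, 53 to 60 days after the 6 g/day month. Two of three follow-up measurement occasions per participant enter no planned comparison. A better analysis of data already collected is available at almost no cost.

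This rests on visits kept as scheduled and on 30-day months. Section 7.3 aims to reschedule a missed visit within 2 weeks, so some 1-month draws could fall after the step-down. The kinetic table is illustrative, and the conclusion does not depend on any one half-life. The randomized comparison of the whole regimen stands as planned.

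**What to change.** In 9.4.1, add the plasma and red-cell omega-3 measures as outcomes in the same GEE approach, with terms for treatment, visit and treatment-by-visit. Report the between-arm difference with a confidence interval at 2 weeks, 1 month and 3 months. Name 1 month as the exposure check for the 6 g/day phase and 3 months as the check for the 1.2 g/day phase.

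State that these are exposure checks and not efficacy endpoints; as such they add no multiplicity burden to the primary markers. The change should stop there: extra visit-specific contrasts on the markers would raise a multiplicity question of their own and are not needed for this point.

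The cost is a few lines of text and a few more model fits. Dose, capsule count, visits, draws and assays stay as they are, because 6.4 already provides the measurements.
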